8.2 Safety Monitoring

Safety assessments will consist of monitoring and recording all adverse events and serious adverse events, the regular monitoring of hematology and blood chemistry parameters and regular physical examinations. Adverse events will be evaluated continuously throughout the study. Safety and tolerability will be assessed according to the NIH/NCI Common Terminology

Criteria for Adverse Events version 5.0 (CTCAE v5) that is available at:
<http://evs.nci.nih.gov/ftp1/CTCAE/About.html>

Protocol Monitoring Committee (PMC);

The PMC monitors its assigned ongoing research protocols for: adverse event reporting, data and safety monitoring, and internal audit findings. The PMC, upon review of any agenda item, may approve the study for continuation, require revisions, suspend or close a protocol.

The PMC meets monthly and reviews accrual, patterns and frequencies of all adverse events, protocol violations and when applicable, internal audit results.

Investigators of studies which are designated to be reviewed by the PMC for data and safety monitoring, shall provide a statistical report of the study's progress and summary of adverse events and deviations based on the phase of the study and the associated risk of the study or more often if applicable.

8.2.1 Internal Monitoring Plan

Data will be captured in OnCore, Moffitt's Clinical Trials Database.

Regulatory documents and case report forms will be monitored internally according to Moffitt Cancer Center Monitoring Policies. Monitoring will be performed regularly by the MCC Clinical Monitoring Core for accuracy, completeness, and source verification of data entry, validation of appropriate informed consent process, reporting of SAEs, and adherence to the protocol, Good Clinical Practice (GCP) guidelines, and applicable regulatory requirements.

8.3 Reporting of Serious Adverse Events

All AEs will be recorded on the appropriate CRF. The Investigator will also identify the date of onset, date of resolution, seriousness, outcome, and the relationship to study drug. Every effort should be made to determine the cause of each AE and whether or not it is related to the study drugs. The relationship of the AE to the study drug must be rated and recorded following the guidelines outlined in the CTCAE v5. All the AEs will be reviewed by the Principal Investigator of the study. The 2 categories for AE grading are:

- 1. Definite**
- 2. Probable**
- 3. Possible**
- 4. Unlike**
- 5. Unrelated**

The definition of serious adverse events (SAEs) is given in Section 8.1.1.

Each serious adverse event must be followed up until resolution or stabilization, by submission

of updated reports to the designated person. An isolated laboratory abnormality that is assigned grade 4, according to CTC definition, is not reportable as an SAE; unless the investigator assesses that the event meets standard ICH criteria for an SAE. CTC grade 4 baseline laboratory abnormalities that are part of the disease profile should not be reported as an SAE, specifically when they are allowed or not excluded by the protocol inclusion/exclusion criteria.

To ensure patient safety, each serious adverse event must be reported to [name] expeditiously. Moffitt Cancer Center will report SAEs by completing an SAE report in OnCore, the electronic data capture system. If applicable, the site should also follow protocol guidelines for additional reporting to government agencies.

When required, and according to local law and regulations, serious adverse events must be reported to the Ethics Committee and Regulatory Authorities.

All serious adverse events should be reported to Taiho Drug Safety or Designee within 24 hours from the time that the investigator first becomes aware of the SAE. Comprehensive information available at the time of initial reporting (including narrative description, medical history and concomitant medications) needs to be provided with careful considerations regarding causality and serious criterion. In the event of such an event, the investigator should refer to the Pharmacovigilance section of the contract for reporting procedures.

Taiho Drug Safety: (email or by fax). This can be performed by faxing it to Taiho or designee at [contact] or via e-mail at [contact] (please note the underscore between '102' and 'Safety').

8.4 Pregnancies

Although pregnancy and lactation are not considered adverse events, it is the responsibility of investigators or their designees to report any pregnancy or lactation in a subject (spontaneously reported to them) that occurs during the trial.

Pregnancies and lactations that occur after the consent form is signed but before treatment allocation/randomization must be reported by the investigator if they cause the subject to be excluded from the trial, or are the result of a protocol-specified intervention, including but not limited to washout or discontinuation of usual therapy, diet, placebo treatment or a procedure.

Pregnancies and lactations that occur from the time of treatment allocation/randomization through 120 days following cessation of treatment, or 30 days following cessation of treatment if the subject initiates new anticancer therapy, whichever is earlier, must be reported by the investigator. All reported pregnancies must be followed to the completion/termination of the pregnancy. Pregnancy outcomes of spontaneous abortion, missed abortion, benign hydatidiform mole, blighted ovum, fetal death, intrauterine death, miscarriage and stillbirth must be reported as serious events (Important Medical Events). If the pregnancy continues to term, the outcome (health of infant) must also be reported.

Such events must be reported within 24 hours to the Principal Investigator. Within 24 hours of the Investigator becoming aware, the pregnancy must be reported to Taiho Drug Safety or Designee using the Pregnancy Form New and/or corrected information regarding the pregnancy obtained after submitting the initial Pregnancy Form must be submitted by faxing an updated Pregnancy Form to Taiho Pharmacovigilance or designee. **This can be performed by faxing it to Taiho or designee at [contact].**

9. Statistical Methods and Data Analysis

9.1 Definition of Study Endpoints

To meet the objectives for this study, data for the following endpoints will be collected:

- Safety and Tolerability
- Tumor response by RECIST 1.1 (Secondary)
- Exploratory biomarkers and cytokine multiples assay (Exploratory)

9.2 Determination of sample size

The primary objective of this study is overall survival at 6 months. Overall survival (OS) will be defined as the time from starting on trial to date of death due to any cause. Dropouts/screen failures defined in section 4.3.1. Patients will be considered inevaluable for the primary endpoint of 6 months of overall survival if they are not able to complete first cycle or if they are lost follow-up prior to 6 months from starting on trial except death. Inevaluable patients will be replaced. The study will test the null hypothesis of $\leq 45\%$ of OS at 6 month against the alternative of $\geq 70\%$ of OS at 6 month. The sample size was determined based on the Simon's two-stage minimax design. With one-sided 10% of type I error rate and 90% power, a sample of evaluable 25 patients will be evaluated; 15 in first stage and additional 10 patients in second stage. If 7 or more out of 15 survive 6 months or more, the study goes on the second stage. The experimental treatment will be deemed to have good activity if ≥ 15 out of 25 patients survive 6 months or more. We will continue to recruit patients during interim analysis

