This is a single institutional phase II single arm, two-stage trial using ramucirumab and TAS 102 in subjects with advanced, refractory gastric or GEJ adenocarcinoma. In the first stage, 15 patients will be accrued. If 7 or more out of 15 survive 6 months or more, an additional 10 patients will be accrued for a total of 25 patients. TAS 102 and ramucirumab will be concurrently administered with ramucirumab 8mg/kg every 2 weeks (Q2W) and TAS 102 at doses of 35 mg/m² twice a day (Details on 5.1). After 2 cycles (1 cycle=28 days), response and progression will be evaluated using Response Evaluation Criteria in Solid Tumors (RECIST) guidelines (version 1.1). Primary endpoint is 6 month overall survival. We will continue to recruit patients during interim analysis. Although no dose limiting toxicities of TAS 102 plus bevacizumab which has almost same mechanisms of action and safety profiles as ramucirumab were observed in a previous phase 1/2 study ⁴⁴, unexpected toxicities can occur with this combination. Therefore, we will closely monitor first 6 patients for first 28 days. If none or one of these patients has a dose limiting toxicity, we will continue without dose adjustment. If ≥ 2 patients has a dose limiting toxicity, the dose will be decreased to level -1 (TAS 102: 30mg/m² twice a day and ramucirumab: 8mg/kg Q2W, details in table 1), and 6 additional patients will be enrolled at dose level -1. If none or one of these patients has a dose limiting toxicity at dose level -1 for first 28 days, we will use dose level -1. If ≥ 2 patients has a dose limiting toxicity at dose level -1, the study will be terminated. First 6 or 12 patients depending on dose limiting toxicities will be used for primary and secondary objectives. Dose limiting toxicity is defined as a grade 3 or higher non-hematological toxicity excluding controllable nausea, vomiting, hypertension, diarrhea, transient electrolyte abnormalities and alopecia; grade 4 neutropenia

lasting 7 days or more; grade 3 or higher febrile neutropenia; grade 4 thrombocytopenia.

4. Eligibility

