4.3.1 Screen Failures/Dropouts/Replacements

A subject who discontinues study participation prematurely for any reasons except death, disease progression and severe toxicity is defined as a dropout.

A subject who, for any reason (e.g., failure to satisfy the selection criteria), terminates the study before the time point used for the definition of "dropout" (see above) is regarded a "screening failure".

Subjects who withdraw from treatment (for any reason) may be replaced.

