9.3 Statistical analysis

Overall survival (OS) is defined as the time from starting on trial to date of death due to any cause and progression-free survival (PFS) is defined as the duration of time from start of treatment to time of progression or death, whichever comes first. The final analysis will be conducted after the follow-time of the last patient exceeds 6 months. The primary endpoint of the study is OS at 6 month. The experimental treatment will be deemed to have good activity if ≥ 15 out of 25 evaluable patients survive 6 months or more. OS will be estimated using the Kaplan-Meier method and the two-sided 95% confidence interval (CI) for median OS will be computed using log-log transformation.

The secondary endpoints in this study include toxicity, PFS and the objective response rate (ORR) defined as (complete response (CR) + partial response (PR)) using RECIST 1.1 criteria (Appendix A). ORR will be reported with 95% CI computed by the Clopper-Pearson method. The frequency and severity of adverse events and tolerability of the regimen will be summarized using descriptive statistics. PFS with 95% CI will be estimated. As exploratory objective, the association between biomarkers and clinical outcomes (ORR, OS and PFS) will be examined using multiple logistic regression and the multivariable Cox regression model. A p-value of <0.05 will be considered statistically significant. Frequency and severity of adverse events will be summarized using descriptive statistics.

10. Data Recording

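### Patients who cannot complete cycle 1 are dropped from the 6-month survival count and replaced, so the 7/15 and 15/25 rules can overstate survival among all treated patients

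*Combined protocol and SAP*

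**What the plan says.** Section 9.2 defines the endpoint without reference to treatment completion: "Overall survival (OS) will be defined as the time from starting on trial to date of death due to any cause". It then adds an evaluability rule. The first limb is "Patients will be considered inevaluable for the primary endpoint of 6 months of overall survival if they are not able to complete first cycle"; the second covers patients who are "lost follow-up prior to 6 months from starting on trial except death". The consequence is "Inevaluable patients will be replaced". What counts as being unable to complete the cycle is not defined. Section 9.3 sets the success criterion as at least "15 out of 25 evaluable patients survive 6 months or more".

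Other sections treat the same patients differently:

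- **Section 4.3.1:** "A subject who discontinues study participation prematurely for any reasons except death, disease progression and severe toxicity is defined as a dropout". The same section then says: "Subjects who withdraw from treatment (for any reason) may be replaced".
- **Section 4.3.2** requires replacement of dropouts. It also requires replacement of patients who stop without a response evaluation, but not when the reason is a drug-related adverse event or disease progression.
- **Sections 3 and 5.1**, on the safety lead-in: "First 6 or 12 patients depending on dose limiting toxicities will be used for primary and secondary objectives". No condition about completing cycle 1 is attached.
- **Section 4.3** asks patients who discontinue to remain in survival follow-up, unless they withdraw consent for all procedures or lose the ability to consent freely.

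**The concern.** The primary objective is 6-month survival in patients receiving the combination. Completing a 28-day cycle is known only after treatment has started, and it may be related to survival: toxicity, early progression and early death can all prevent it. A patient whose vital status at 6 months is known gives a valid observation of all-cause survival whatever happened in cycle 1, so there is no statistical reason to discard that patient.

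The rule acts at both stages, on the 7-of-15 gate and on the final 15-of-25 criterion. If removed patients die sooner than the others, an inactive regimen has a better chance of passing both. The trial is open-label and the condition is undefined, so deciding who counts also involves judgement after the fact.

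The protocol does not say whether 45% and 70% describe all treated patients or only those who complete cycle 1. In the first case the error rate is at stake. In the second the error rate holds, but the conclusion leaves out people who start the regimen and cannot continue.

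**Working it through.** **Inputs from the protocol (synopsis, Sections 9.2 and 9.3).** Null rate 0.45, alternative 0.70, one-sided type I error 10%, power 90%, 15 patients in stage 1 and 10 in stage 2, continue if at least 7 of 15 are alive at 6 months, success if at least 15 of 25 are.

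**Step 1: reproduce the design.** With true rate p in the counted patients,

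P(success) = Σ over x = 7 to 15 of P(Bin(15, p) = x) × P(Bin(10, p) ≥ 15 − x).

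- p = 0.45: 0.0951 (type I error)
- p = 0.70: 0.9004 (power)
- P(Bin(15, 0.45) ≥ 7) = 0.5478 (chance of passing the stage 1 gate under the null)

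The stated design is correct as arithmetic. The margin below the 10% limit is about half a percentage point.

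**Step 2: effect of the exclusion.** Let q be the share of treated patients who do not complete cycle 1 and s their 6-month survival. Neither is in the protocol, so both are assumed. If all-treated survival is at the null value,

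0.45 = (1 − q) × p_e + q × s, so p_e = (0.45 − q × s) / (1 − q),

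where p_e is the rate among evaluable patients. Two examples:

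- q = 0.10, s = 0.20: p_e = (0.45 − 0.02) / 0.90 = 0.4778
- q = 0.10, s = 0: p_e = 0.45 / 0.90 = 0.5000

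Entering p_e in the Step 1 formula gives the type I error for all-treated survival:

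| Non-completers alive at 6 months (s) | q = 2% | q = 5% | q = 10% |
|---|---|---|---|
| 50% | 9.3% | 9.1% | 8.6% |
| 45% | 9.5% | 9.5% | 9.5% |
| 40% | 9.7% | 10.0% | 10.5% |
| 20% | 10.4% | 12.0% | 15.2% |
| 0% (extreme) | 11.2% | 14.2% | 21.0% |

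The chance of passing the 7-of-15 gate rises from 54.8% to 58.9% (s = 20%) or 62.1% (s = 0) at q = 5%, and to 63.3% or 69.6% at q = 10%.

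**Step 3: what the success threshold can conceal.** If two patients were replaced and both died before 6 months, 15/25 = 60.0% among evaluable patients is 15/27 = 55.6% among all treated. With three it is 15/28 = 53.6%.

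**Step 4: compare the sections for one patient.** Take a patient who stops in cycle 1 because of a drug-related adverse event, has no response evaluation, and dies in month 3.

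- Section 9.2: inevaluable and replaced.
- Section 4.3.1: not a dropout if the toxicity was severe, but may be replaced, since any withdrawal from treatment qualifies.
- Section 4.3.2: its response-evaluation rule gives no ground for replacement.
- Sections 3 and 5.1: used for the primary objective if in the lead-in group.

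The same patient can be a failure under one section and absent from the count under another.

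**The case against.** The sentence just before the evaluability rule in 9.2 refers to 4.3.1 for dropouts and screen failures, and 4.3.1 keeps death, progression and severe toxicity out of the dropout definition. If those limits were meant to govern evaluability, most outcome-related removals would disappear. But 9.2 does not say so, its own rule carries no such limits, and 4.3.1 also allows replacement whatever the reason for withdrawal.

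The exception for death in 9.2 might be read as applying to both limbs. Deaths in cycle 1 would then count as failures, and the 0% row of the table would be less credible. A patient who stops alive in cycle 1 and dies later would still be removed, so the bias would be smaller but not gone.

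Two of the conflicts admit a milder reading. The response-evaluation rule in 4.3.2 may concern response only, and the lead-in sentence may mean simply that those patients count toward the 25. Nothing in the text settles either reading.

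The synopsis says 6-month survival will be estimated by Kaplan-Meier, and the protocol does not confine that estimate to evaluable patients. An all-treated estimate is therefore not ruled out, but none is specified and it does not govern the decision count.

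The size of the effect rests wholly on assumed inputs. Eligibility requires ECOG 0 or 1 and a life expectancy above 3 months, which should limit early failure. With 40% of non-completers alive and no more than 5% non-completion, the error stays just within 10%. That point stands: material bias is possible but not demonstrated.

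Finally, Section 6.7 starts survival contacts only after confirmed progression or new anti-cancer therapy. A patient who stops for toxicity alone has no stated survival contact after the 30-day safety visit. This also stands, and the fix has to close that gap.

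**Conclusion.** The concern holds and should be corrected before the decision rule is relied on. Followed as written, Section 9.2 removes from an all-cause survival endpoint patients whose outcome can be known, on a condition that arises after treatment starts, and it conflicts with other sections on replacement. This follows from the text and needs no assumption.

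Its numerical effect does need assumptions. If 45% is the all-treated rate and non-completers survive less often, the type I error exceeds the design's 9.5%: 12.0% to 14.2% at 5% non-completion and 15.2% to 21.0% at 10%, for 20% down to 0% of non-completers alive. It is unchanged if their survival is also 45%, and falls to 8.6% if 50% are alive at 10% non-completion. If 45% is instead the rate among completers, the error stays at 9.5% but the claim covers completers only.

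**What to change.** 1. In Sections 9.2 and 9.3, define the primary population as all patients who receive at least one dose, and state that 45% and 70% refer to it.
2. Count every dosed patient with known 6-month vital status, alive or dead, whatever happened in cycle 1. Do not replace for an incomplete cycle 1. Replacement may remain, for the count rule only, when vital status is truly unknown.
3. Reconcile Sections 3, 4.3.1, 4.3.2, 5.1 and 9.2 on who is counted and who is replaced.
4. Record 6-month vital status for every treated patient, including those who stop for toxicity without progression, and align Section 6.7 with this. Report the all-treated Kaplan-Meier 6-month survival with its confidence interval, censoring patients lost to follow-up. The evaluable-only result can be kept as a sensitivity analysis.

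**Cost.** If 45% and 70% describe all treated patients and vital status is complete, N stays 25, both thresholds stand, type I error is 9.5% and power 90.0%. Observed survival may look less favourable.

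If the two rates describe completers, counting everyone lowers the rate under the alternative to 0.70 × (1 − q) + q × s. Power becomes 81.5% at q = 5% and 69.9% at q = 10% when no non-completer survives, or 84.3% and 76.8% when 20% do. The sponsor should therefore name the population and restate the power.

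Counting unknown vital status as not alive, instead of replacing, is not what is proposed here. It would reduce power to 87.0%, 81.5% and 69.9%, and type I error to 8.0%, 6.2% and 3.8%, at 2%, 5% and 10% unknown, assuming loss is unrelated to survival.
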